#### 5.0 Inclusion/Exclusion Criteria

#### Inclusion Criteria:

- Documented diagnosis of PAH, defined as mPAP > 25 mm Hg and PWP ≤ 15 mm
   Hg,
- IPAH, HPAH, or PAH associated with collagen vascular disease, repaired congenital heart disease, or appetite suppressant use.
- World Health Organization (WHO) functional class I, II, or III, stable for at least 8
  weeks prior to enrollment.
- Hemodynamically stable without evidence of right heart failure. Hemodynamic stability will be defined as having a normal right atrial pressure (≤10 mm Hg) and cardiac index (≥2.5 l/min) with no more than mildly impaired right ventricular function on echocardiogram.
- 6MW distance, as performed at screening or within 12 weeks prior to screening, of
   330 meters
- Mean blood pressure of >60 mmHg
- Receiving stable doses of one or more medications that are approved for treatment
  of PAH, including endothelin receptor antagonists, phosphodiesterase 5 inhibitors,
  and prostanoids, for a minimum of 12 consecutive weeks before enrollment. Note:
  Anticoagulant therapy can be adjusted according to target INR,
- Diuretic dose stable for 8 weeks.
- 18 years of age or older
- Willing and able to complete an informed consent form.
- Sexually active subjects must be willing to use an acceptable method of contraception while participating in the study.
- Females of childbearing potential must have a negative pregnancy test at screening, using accepted birth control, and be willing to have additional pregnancy tests during the study.

#### Exclusion Criteria

- Previous treatment with any formulation of rhACE2.
- Known allergy or hypersensitivity to rhACE2.
- History of systemic hypotension, defined as systolic BP < 90 mm Hg and/or diastolic BP <60 mm Hg.

- Hospitalization for PAH associated deterioration in the previous 6 months
- Use of any investigational product or device within 30 days prior to dosing, or known requirement for any investigational agent prior to completion of all scheduled study assessments.
- Known to be positive for human immunodeficiency virus (HIV), Hep B, or Hep C or with cirrhosis from any cause.
- Any additional medical condition, serious intercurrent illness, or other extenuating circumstance that, in the opinion of the Investigator, may significantly interfere with study compliance, including all prescribed evaluations and follow-up activities.
   Concurrent disease or condition that may interfere with study participation or safety include bleeding disorders, arrhythmia, organ transplant, organ failure, current neoplasm, poorly controlled diabetes mellitus, and serious neurological disorders.
- Complex congenital heart disease
- Estimated GFR <60mL/min/1.73m² or hepatic enzyme levels more than 2 times the upper limit of normal.
- Pregnant or lactating at screening, or planning to become pregnant (self or partner) at any time during study.
- Weight >75kg.
- Any bleeding concerns as evidenced by INR > 1.5 (in patients not receiving anticoagulation therapy) or platelet count < 80,000

- Hematocrit < 30%

- Any use of an ACE inhibitor or angiotensin receptor blocker within 7 days of enrollment

#### 6.0 Enrollment/Randomization

Participants will be recruited from the Pulmonary Hypertension Clinic at Vanderbilt Medical Center. All patients seen at our clinic meeting eligibility requirements will be approached for participation.

#### 7.0 Study Procedures

#### 7.1 Physical Examination and Medical History

Physical examination will be performed to ensure suitability according to the inclusion and exclusion criteria at screening and baseline and to document the health status at the time points specified in the Schedule of Events (Appendix 1). The physical examination comprises measurement of height and body weight (at screening only), vital signs including blood pressure, heart rate, respiratory rate, and oxygen saturation, and a routine medical examination. Functional Class will also be assessed at this time.

A medical history will be recorded at screening only. The medical history will elicit information concerning existing medical conditions, major illnesses, and related surgical procedures. Any prescribed or over-the-counter medications that the subject received within the past 30 days should be recorded on the case report form (CRF). Medication prescribed for the treatment of PAH for the 12 weeks prior to enrollment should be recorded on the CRF. Subjects will be instructed to notify the primary investigator or study coordinator before beginning new prescribed or over-the-counter medications.

#### 7.2 Blood Pressure

Systolic and diastolic systemic BP will be measured by means of either a standard manual or an automatic BP measuring device (cuff method). For each subject, the same method should be used during the entire study, and the type of device used should be recorded on the CRF. The same arm will be used for each measurement of BP, and BP will be measured after 5 minutes seated.

#### 7.3 Pulse Oximetry (Oxygen Saturation) and Heart Rate

Heart rate (HR) and oxygen saturation will be measured by pulse oximetry after the subject has been at rest for at least 5 minutes. Pulse oximetry provides a non-invasive method of monitoring the percentage of hemoglobin, which is saturated with oxygen. The pulse oximeter consists of a probe attached to the subject's finger or ear lobe, which is linked to a computerized unit. The unit displays the percentage of hemoglobin saturated with oxygen and the calculated HR and has an audible pulse signal and user-programmable, audible alarms. An oximeter detects hypoxia before clinical signs of cyanosis can be detected.

#### 7.4 Six-Minute Walk Test and Borg Dyspnea Scoring

The 6MW test is a submaximal exercise test that is widely used as an outcome and safety measure in clinical trials and cardiopulmonary rehabilitation (American Thoracic

Society 2002, Am J Respir Crit Care Med) (Hoeper 2004, J Am Coll Cardiol). The test is simple and inexpensive, could likely be applied to the elderly, the frail, and those with walking difficulties. Furthermore, the test might reflect more accurately the activities undertaken in normal life than physiological measurements at peak exercise. During this test the subject is asked to walk along a prescribed path (typically 30 meters long) as far as possible during a 6-minute interval. The subject may walk at whatever pace is comfortable, with the goal of walking the longest distance possible. The subject may rest as needed.

Borg scales are used in practice and in clinical studies as a reliable way to help assess the rate of exertion as perceived by the patient or subject (Grant 1999, Chest) (Mador 1995, Chest). The scale consists of a vertical scale labeled 1 through 10, with text descriptors that express correspondingly increased intensity of effort at fixed points along the scale. In this study, the Borg scale will be used to assess the degree of discomfort evoked by breathing and the degree of effort required to breathe, as reported by the subject after the 6MW test.

#### 7.5 Electrocardiogram

In subjects with PAH, the electrocardiogram (ECG) typically reveals right axis deviation and right ventricular (RV) hypertrophy. The standard 12-lead ECG will be recorded while the subject is resting in supine position. The following parameters will be assessed: HR, RR, PQ, QRS, QT and QTc. Additionally, the occurrence of de- or repolarization disorders, arrhythmic disorders or other abnormalities will be assessed and obvious changes of ECG parameters compared to the baseline record will be commented upon. ECGs will be interpreted locally. Changes to the ECG will be coded by the Investigator as clinically significant or not clinically significant. Clinically significant changes will be reported as AEs. Original printouts will be archived within the subject file and ECG recording results will be noted in the subject's CRF.

#### 7.6 **Echocardiogrophy**

Two-dimensional (2D) and Doppler echocardiography will be performed using standard techniques on commercially available equipment with a predefined imaging protocol. Images will be obtained with the subjects in the left lateral position. The maximal tricuspid regurgitant jet (TRJ) velocity will be assessed by determining the peak regurgitant velocity (v) in the continuous-wave Doppler flow profile obtained from the cardiac apex. The tricuspid valve pressure gradient (TPG) (i.e., the pressure difference

between the right ventricle and right atrium during systole) will be calculated by applying the modified Bernoulli equation. Pulmonary arterial systolic pressure will be calculated using the formula  $4v^2$  + right atrial pressure. Right atrial pressure will be assessed by clinical examination of the jugular venous pressure, and echocardiographic diameter of the inferior vena cava and its change with inspiration.

The right atrial volume is calculated at end systole from the apical four chamber view using the diameter and the long axis length of the atrium according to the equation: Volume = (7(pi x D²L)/6, where D = minor axis (cm), L = major or long axis (cm) (Wang 1984, Chest). The eccentricity index, a measure of the degree of septal displacement, will be measured at end diastole and end systole from parasternal short-axis projections of the left ventricle. It is calculated as the ratio of the minor axis of the left ventricle parallel to the septum at the level of the chordae (a), divided by the minor axis perpendicular to and bisecting the septum at the same section (b) (eccentricity index = a/b). The Doppler-derived RV MPI is calculated as described previously by Tei et al (Tei 1996, J.Am.Soc.Echocardiogr.) using the length of two time intervals in the formula (a-b)/b, where a equals the time between the onset of QRS complex and onset of tricuspid inflow and b equals the ejection time of RV outflow. TAPSE will be measured as per protocol (Forfia et al, AJRCCM, 2006).

#### 7.7 Pregnancy Test

Female subjects of childbearing potential will have a pregnancy test (urine) performed at screening and at timepoints specified in the Schedule of Events (Appendix 1). Female subjects with a positive pregnancy test at screening may not be enrolled in the study. Female subjects already enrolled in the study must be terminated from the study if a positive pregnancy test result is obtained at any visit after screening.

#### 7.8 Laboratory Assessments

Routine clinical laboratory parameters (hematology, chemistry, coagulation panel, and urinalysis) as well as the biomarkers BNP and troponin I will be analyzed by the local hospital laboratory.

Ang II/(1-7) ratios in peripheral blood will be measured for analysis. In Phase A only, the transpulmonary Ang II/(1-7) ratio will be measured. Ratio will be analyzed by Wake Forest or GSK.

Urine isoprostanes and isofuranes will be processed in the central lab.

All samples, other than routine labs (SOD2 activity, IDH activity), will be stored at -80°C, batched and analyzed at the conclusion of each dose escalation.

#### Clinical laboratory tests include the following:

Hematology white blood cell count with differential, red blood cell count, platelet

count, hemoglobin, and hematocrit

Standard chemistry

Substrates albumin, total bilirubin, total protein, BUN, creatinine, glucose

Electrolytes calcium, chloride, sodium, phosphorous, potassium

Enzymes aspartate aminotransferase/glutamate oxalo-acetate transaminase

(ASAT/GOT); alanine aminotransferase/glutamate pyruvate

transaminase

(ALAT/GPT); alkaline phosphatase (AP); creatine kinase (CK)

Coagulation panel international normalized ratio (INR)/prothrombin time (PT), PTT

Biomarkers

Array analysis Collection of blood for RNA expression (PAXgene tube) and

cultured lymphocytes (yellow top tube)

Ang II/Ang (1-7) Blood samples for Angiotensin II/ Ang (1-7) ratios:

Protease inhibitor cocktail at 0.05ml/1ml whole blood will be added

to EDTA tubes. Two pink-top 6ml tubes will be collected at

baseline and at 2 hours. The samples will be mixed and

SOD2 activity assay centrifuged at 3000g for 10 minutes. The plasma will be placed into

labeled tubes and frozen at -80°C until shipment to Wake Forest

Hypertension Laboratory or GSK.

Plasma activity assay

Serum, local lab BNP, isoprostanes, isofurans, troponin I, inflammatory biomarkers

(TGFb, IL2).

Urine, central lab 8-isoprostanes and isofuranes

Two frozen urine samples of 10 mL each will be stored in a

specially assigned freezer at -80°C until shipment.

Standard urinalysis appearance, color, pH, specific gravity, ketones, protein, glucose,

bilirubin, nitrite, urobilinogen, sodium, pregnancy (where

appropriate)

Immunogenicity studies

Pharmacokinetic profile To be analyzed by GSK.

#### 7.9 Hemodynamic Assessments

Pulmonary arterial catheters for Phase A will only be placed in patients undergoing standard clinically-indicated right heart catheterization. A pulmonary artery catheter (PAC) will be placed under fluoroscopy in the VU Cath Lab using sterile technique. The PAC is inserted percutaneously into a major vein (jugular, subclavian, femoral) via an introducer sheath.

The measurements that will be assessed include: right atrial pressure (RAP), pulmonary arterial pressure (PAP), pulmonary wedge pressure (PWP), cardiac output (CO), cardiac index (CI), pulmonary vascular resistance (PVR), and pulmonary artery saturation (PAsat).

Hemodynamics measurements will be obtained at baseline in the cardiac catheterization lab has been performed for comparator values.

Blood will be drawn from the mixed venous position and from the wedge position to measure transpulmonary gradient of AngII/(1-7) ratio.

The patient will then be moved to the recovery area. Repeat baseline values will be obtained and rhACE2 will be administered over 30 minutes. Hemodynamic measurements will be repeated and at 30 minutes, 1, 2, 3, and 4 hours post dosing. Transpulmonary gradient blood will be collected at baseline prior to drug administration and at four hours after administration prior to removal of the catheter. The catheter will be removed prior to the subject leaving the cardiac catheterization lab for the CRC. The subject will then be monitored for 20 hours in the CRC.

Variables that will be recorded from the right heart catheterization include right atrial pressure, right ventricular systolic, diastolic and end diastolic pressures, pulmonary artery systolic and diastolic pressure, pulmonary wedge pressure, pulmonary arterial saturation, systemic systolic and diastolic blood pressure, heart rate, systemic arterial saturation measured by pulse oximetry, cardiac output and index measured by either thermodilution or assumed Fick.

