## Supplemental Figure 3.

Patient level data on AngII, Ang-(1-7) and the AngII/Ang-(1-7) ratio just prior to rhACE2 infusion () time point, followed by measreument at 2 and 4 hours.

Supplemental Table 1. ACE2 Activity in PAH vs. Control Patient Demographics

Demographics	
	N=11
Age (years)	43 (12)
Sex (M/F)	2/9
PAH type (H/I)	4/7
6MWD (m)	390.7 (60.0)
PAH therapy (n)	
Parenteral prostaglandin	6
Phosphodiesterase type 5 inhibitor	4
Endothelin Receptor Antagonist	4
Aldosterone antagonist (n)	4

Data are presented as mean (SD) unless otherwise noted. PAH = pulmonary arterial hypertension, H= heritable PAH, I = idiopathic PAH, 6MWD=six minute walk distance.

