## Supplemental Table 7. Hemodynamic Effect of GSK2586881 in PAH

	-1H	0	1H	2H	4H
Systolic BP	112.2 (12.1)	110 (9.7)	110 (11.2)	106.4 (10.2)	106.4 (23.2)
Diastolic BP	68.2 (10.8)	66.2 (5.2)	58.6 (14.6)	55 (5.1)	61.8 (12.6)
Heart Rate	83.6 (11.9)	70.2 (11.2)	76.6 (5.8)	79.4 (8.1)	78.2 (15.4)
sPAP	64.8 (29.5)	61.8 (24.4)	58.4 (18.7)	65.4 (26.7)	60.4 (27.6)
dPAP	29.4 (11.1)	30.2 (8.9)	26.6 (10.8)	27.0 (6.8)	29.8 (7.3)
mPAP	40.6 (13.7)	42.8 (13.8)	41.6 (15.4)	40.2 (13.7)	40.6 (11.7)
PWP	14.2 (2.8)	15.8 (5.0)	15.4 (8.1)	13.5 (10.4)	12 (4.3)
СО	4.2 (1.1)	5.3 (1.4)	5.8 (1.6)	6.1 (1.3)	6.3 (1.5)*
CI	2.66 (0.3)	2.8 (0.6)	3.23 (1.0)	3.4 (0.8)	3.4 (0.7)#
PVR	5.4 (1.9)	4.0 (1.3)	3.5 (1.1)	2.4 (1.9)	3.5 (0.8)

\*p=0.008 vs. 0 and BL time points. #p=0.02 vs. O and BL time points

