# 12 Statistical Considerations

Descriptive statistics will be used to characterize patients at study entry. Dose analysis will be approached using the design below to determine the dose limiting toxicity (DLT). No statistics will be performed specifically on tolerability data. Instead, AEs will be described in their entirety and evaluated by descriptive statistical methods. Despite sample size limitations that hamper statistical inference, analysis of secondary endpoints will be conducted using mixed-effects regression modeling techniques, supported by conditional estimation methods with interaction. For example, the change in pulmonary and systemic hemodynamic measurements according to echocardiogram from baseline to end of study, the change in six minute walk distance (6MWD) from baseline to end of study, and the change in biochemical variables (BNP, NO and SOD2) from baseline to Day 6 and end of study will be assessed to determine the delta in paired comparisons over time.

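### Section 7.9 takes two pre-dose haemodynamic sets and no section fixes which is the reference for catheter-measured change; the choice moves the 4-hour CO change from +50% to +19%

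*Combined protocol and SAP*

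**What the plan says.** Section 7.9 (Hemodynamic Assessments) takes two sets of catheter readings before any drug is given. Of the first it says: "Hemodynamics measurements will be obtained at baseline in the cardiac catheterization lab has been performed for comparator values". The sentence is garbled, but it is the only place where the section calls a set of readings the comparator. The patient is then moved to the recovery area, where "Repeat baseline values will be obtained and rhACE2 will be administered over 30 minutes". Post-dose readings run to 4 hours. The section allows "cardiac output and index measured by either thermodilution or assumed Fick" and does not hold one method fixed within a patient.

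Other places do not settle the matter:

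- **Appendix 2** marks haemodynamics at 0, 1, 2 and 4 hours and leaves the Baseline column empty, which points towards time 0.
- **Section 12** gives as an example "the change in pulmonary and systemic hemodynamic measurements according to echocardiogram from baseline to end of study" and says that such changes "will be assessed to determine the delta in paired comparisons over time". The example concerns echocardiography. No rule is given for catheter readings.
- **Supplemental Table 7** prints columns for -1H, 0, 1H, 2H and 4H. The footnote to CO at 4H reads "p=0.008 vs. 0 and BL time points", and the CI footnote gives p=0.02 against the same two points.

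Section 2.2 makes change in pulmonary and systemic haemodynamics a secondary objective. Section 4.0 describes an open-label dose escalation with no control group.

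**The concern.** Without a control arm, the pre-dose reading is the only stand-in for what would have happened without drug. The plan has two such readings, taken at different moments and in different places. If they differ, an analyst who follows the comparator label counts any pre-drug drift as a drug effect. An analyst who follows the schedule in Appendix 2 does not. With no rule fixed beforehand, the choice can also be made after the results are known. At stake are the size of the acute CO and PVR changes and the direction of the heart-rate change.

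**Working it through.** **Inputs.** All values are group means from Supplemental Table 7. The plan states no expected haemodynamic effect, so there is no planned figure to reproduce.

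**Assumption.** -1H is the cath-lab set and 0 is the repeat pre-infusion set. No text says so outright. It is inferred because 7.9 describes just two pre-dose sets, the table footnotes separate BL from 0, and the legend of Supplemental Figure 3 places its first peptide sample "just prior to rhACE2 infusion".

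**Step 1. Change to 4H under each reference.** Change = value at 4H minus reference; percentage = change / reference.

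| Measure | -1H | 0 | 4H | From -1H | From 0 |
|---|---|---|---|---|---|
| CO | 4.2 | 5.3 | 6.3 | 2.1/4.2 = +50.0% | 1.0/5.3 = +18.9% |
| PVR | 5.4 | 4.0 | 3.5 | -1.9/5.4 = -35.2% | -0.5/4.0 = -12.5% |
| CI | 2.66 | 2.8 | 3.4 | 0.74/2.66 = +27.8% | 0.6/2.8 = +21.4% |
| Heart rate | 83.6 | 70.2 | 78.2 | -5.4 | +8.0 |
| mPAP | 40.6 | 42.8 | 40.6 | 0.0 | -2.2 |

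The heart-rate sign also reverses at 1H (76.6: -7.0 or +6.4) and at 2H (79.4: -4.2 or +9.2). The mPAP row shows that moving to time 0 does not shrink every effect.

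**Step 2. Share of the change that came before drug.** Share = (value at 0 - value at -1H) / (value at t - value at -1H). Rounding ranges move each mean by 0.05.

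- CO: 1.1/2.1 = 52% at 4H (48 to 57%); 1.1/1.9 = 58% at 2H; 1.1/1.6 = 69% at 1H.
- PVR: 1.4/1.9 = 74% at 4H (68 to 79%) and at 1H, but 1.4/3.0 = 47% at the 2H low of 2.4 (43 to 50%).
- CI: 0.14/0.74 = 19% at 4H.

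**Step 3. Do CO and CI agree?** CO/CI implies body surface area, which cannot change in an hour: 4.2/2.66 = 1.58 at -1H, then 1.89, 1.80, 1.79 and 1.85. The -1H pair does not fit the rest. A change of CO method carried through to CI would leave the ratio unchanged. More likely causes are different patients contributing, CO and CI taken by different methods, or transcription; the documents do not say which.

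Applying the later ratios to the -1H CI gives a CO of 1.79 x 2.66 = 4.76 up to 1.89 x 2.66 = 5.03. The pre-dose CO share at 4H then falls to (5.3 - 4.76)/(6.3 - 4.76) = 35%, down to (5.3 - 5.03)/(6.3 - 5.03) = 21%. The 4H change from -1H becomes 6.3/4.76 = +32%, down to 6.3/5.03 = +25%, still above the +19% from time 0.

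**Step 4. PVR from the means.** (mPAP - PWP)/CO gives 26.4/4.2 = 6.29 at -1H, 27.0/5.3 = 5.09 at 0, 26.7/6.1 = 4.38 at 2H and 28.6/6.3 = 4.54 at 4H. The pre-dose share is then 68% at 4H and 62% at 2H. PVR from means need not equal mean PVR, so the gap from the printed values is not in itself an error. The printed 2H PVR still needs care: the 2H PWP of 13.5 is the only pressure mean that is not a multiple of 0.2, as five patients would give, so fewer patients may contribute there. PVR also inherits the doubt about CO at -1H.

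**Not checkable.** The available text gives no n for Table 7 and no within-patient correlations, so neither p-value can be verified. One p-value is printed for two CO contrasts of different size, +1.0 and +2.1.

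**The case against.** A reader might infer that the plan has settled on the cath-lab baseline, and that about half the CO rise and three quarters of the PVR fall were therefore credited to rhACE2 although they preceded it. The documents do not support that.

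- The comparator label rests on one garbled sentence. The same section requires the repeat set, and Appendix 2 marks time 0.
- Table 7 shows both columns openly and reports CO and CI against both. PVR and heart rate carry no significance mark, so the table claims no effect on either.
- The Section 12 example is an echo comparison to end of study, when the catheter is long out. It does not show catheter change being analysed from the wrong baseline.
- The shares are ratios of group means with wide SDs. The CI share of 19% conflicts with 52% for CO, and the PVR share is 47% at 2H.
- The cause of the drift (procedure, setting, method or chance) is not documented.
- The primary objective is safety, escalation depends on dose-limiting toxicities, and the named activity check is the peptide ratio. No decision rule uses CO or PVR.

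All of this stands, and it limits both the claim and its severity. It does not remove the gap: two pre-dose sets exist, only one is called the comparator, and no text gives the reference for catheter change. Printing both contrasts is a defensible display, but it does not say which is the estimate of effect.

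**Conclusion.** The reference for catheter-measured change is undefined, and the one label the text offers points to the earlier, less suitable set. If -1H is the cath-lab set and 0 the repeat set, the 4H group-mean effects depend materially on the choice for CO, PVR and heart rate, and less so for CI (Step 1). The heart-rate reversal does not depend on how CO was measured.

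The pre-dose share should not be stated as one firm number. At 4H it is 52% for CO (about 21 to 35% if the -1H CO is out of line with the -1H CI), 74% for PVR (47% at 2H) and 19% for CI. Severity is moderate: a named secondary objective is affected; the safety assessment and the escalation rules are not.

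**What to change.** State in 7.9 and in Section 12 that the primary reference for every catheter-measured change is the repeat set taken immediately before infusion. Section 12 needs its own sentence on catheter data, since its present example covers only echocardiography. The reason to give is design, not results: as 7.9 describes it, this set is nearest to dosing and follows the move to the recovery area, as the post-dose readings do.

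Define time 0 as pre-infusion for haemodynamics. In Appendix 2 the same column also carries a PK sample that the footnote times at the end of infusion.

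Require the same CO method at all time points within a patient, and record which was used. Report the -1H to 0 change separately as no-drug drift. Show change from the cath-lab set only as a secondary display, with n at each time point. Check the -1H CO and CI against source records.

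Cost: a few sentences, plus one procedural rule on CO method; no new data. The downside is smaller headline CO and PVR effects.
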